## 4.2.2.1.2 Maximum Overall Intensity

Maximum overall intensity is derived from the daily intensities computed as described in Section 4.2.2.1.1 and is calculated as the maximum of the daily intensities over the period considered.

Note: The maximum intensity could be considered "None" (not a reaction) in the analysis despite being considered a reaction by the investigator (eg, swelling measurement > 0 mm but < 25 mm in adults).

#### 4.2.2.1.3 **Presence**

Presence is derived from the maximum overall intensity over the time period considered:

- None: No presence
- Grade 1, Grade 2, or Grade 3: Presence
- Missing or Unknown: Missing presence

Participants with at least one non-missing presence for a specific endpoint will be included in the analysis. Conversely, those without a non-missing presence will not be included in the analysis of the endpoint.

The time period is displayed as follows:

- Injection site reactions: D1-D4, D5-D8, D9 or later
- Systemic reactions: D1-D4, D5-D8, D9-D15, D16 or later.

## 4.2.2.1.4 Time of Onset

Time of onset is derived from the daily intensities computed as described in Section 4.2.2.1.1. It corresponds to the first day with intensity of Grade 1, Grade 2, or Grade 3.

Note: If a reaction is not continuous (ie, reaction occurs over two separate periods of time intervened by at least one daily intensity Missing or None) then the time of onset is the first day of the first occurrence.

Time of onset period is displayed as follows:

- Injection site reactions: D1-D4, D5-D8
- Systemic reactions: D1-D4, D5-D8, D9-D15.

#### 4.2.2.1.5 Number of Days of Occurrence During the Solicited Period

Number of days of occurrence over the period considered is derived from the daily intensities computed as described in Section 4.2.2.1.1. It corresponds to the number of days with daily intensities of Grade 1, Grade 2, or Grade 3. Number of days of presence on the solicited period with a specified intensity may also be derived.

Number of days of occurrence during the solicited period will be displayed by categories as follows:

- Injection site reactions: 1-3 days, 4-7 days, 8 days
- Systemic reactions: 1-3 days, 4-7 days, 8-14 days, 15 days

#### 4.2.2.1.6 Overall Number of Days of Occurrence

If a reaction is ongoing at the end of the solicited period, then the overall number of days of occurrence is derived from the daily intensities and the end date of the reaction after the end of the solicited period. The overall number of days of presence is:

• (End date – investigational vaccination date) + (number of days of presence within the solicited period) - length of the solicited period + 1

If the end date is missing or incomplete (contains missing data), the overall number of days of presence will be considered as Missing.

Overall number of days of occurrence will be displayed by category (range) as follows:

- Injection site reactions: 2-3 days, 4-7 days, 8 days or more, missing end date
- Systemic reactions: 2-3 days, 4-7 days, 8-14 days, 15 days or more, missing end date

#### 4.2.2.1.7 Ongoing

Ongoing is derived from the last daily intensity of the solicited period computed as described in Section 4.2.2.1.1 and the maximum intensity on the ongoing period. The investigator's ongoing flag is not used because the measurement would determine the ongoing status of the reaction.

- Ongoing: if the last daily intensity of the solicited period is at least Grade 1 and the maximum intensity on the ongoing period is at least Grade 1
- Not ongoing: if the last daily intensity of the solicited period is None or the maximum intensity on the ongoing period is None.
- Missing: all other conditions (in this case, it is not included in the denominator of the ongoing analysis in the safety tables).

## 4.2.2.2 Unsolicited AEs

#### 4.2.2.2.1 **Presence**

An observation will be considered an event if it has at least a verbatim term and is not a Grade 0 intensity event.

Grade 0 events will not be included in safety analysis but will be included in separate listings.

## 4.2.2.2.2 Intensity

Intensity will be derived according to the following classification: None, Grade 1, Grade 2, Grade 3, or Missing

If the unsolicited AE is measurable and its preferred term is part of the list of solicited reactions, then the measurement is derived based upon and following the same rule of the intensity scales defined in the protocol for that measurable injection site or systemic reaction. Note the intensity could be considered as "None" (not a reaction) in the analysis despite being considered a reaction by the investigator (eg, swelling measurement >0 mm but < 25 mm in adults).

Intensity for the other unsolicited AEs will correspond to the value reported in the CRF.

The maximum intensity corresponds to the highest intensity for a unique term.

## 4.2.2.2.3 Last Vaccination

Last vaccination before an unsolicited AE is derived from the start date of the unsolicited AE provided in the CRF and is calculated as follows:

• If an unsolicited AE has a complete start date and different to any of the vaccination dates, the start date is used to determine the last vaccination before the unsolicited AE

If the start date is missing or partially missing, or equal to any vaccination date, then the visit number in the "Appeared after Visit" or similar field, is used to determine the last vaccination before the unsolicited AE.

## 4.2.2.2.4 Time of Onset

Time of onset is derived from the start date of the unsolicited AE and the date of last vaccination as described in Section 4.2.2.1.1:

Time of Onset = start date of the unsolicited AE - date of last vaccination before the unsolicited AE + 1.

The time of onset is considered as missing only if one or both dates are missing or partially missing.

The unsolicited AEs will be analyzed "Within 28 days" after each vaccination, which corresponds to AEs with a time of onset between 1 and 29 days. An AE with missing time of onset will be

considered to have occurred just after the last vaccination (computed according to the Section 4.2.2.2.4), so will be included in these tables.

Time of onset period is displayed as D1-D4, D5-D8, D9-D15, D16 or later, and Missing.

**Note:** Unsolicited AE that occurred before vaccination (negative time of onset) or with a time of onset higher than defined above will not be included in analysis but will be listed separately.

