# 7 Discontinuation of Study Intervention and Participant Discontinuation/Withdrawal

# 7.1 Discontinuation of Study Intervention

Not applicable as there is only one vaccination.

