## 4.2.2.4 SAEs

An event will be considered as a serious event if "Yes" is checked for "Serious" in the CRF.

SAEs will be analyzed throughout the study using the following periods:

- Within 28 days after a vaccination
- During the period from 29 days after the injection until the last participant contact at M6
- During the study for related SAEs (ie, all related SAEs occurred during the study)

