#### 5.3.2.5 Start Date and Stop Date

Missing or partially missing start dates or end dates for unsolicited AEs (including SAEs) will remain missing and not be imputed. If the start date is missing or partially missing, the time of onset will be considered to be missing. Nevertheless, unsolicited AEs with missing time of onset will be included in analyses according to the last vaccination (computed according to the Section 4.2.2.2.3),. If either the start date or end date is missing or partially missing, the duration will be considered missing.

Missing or partially missing end dates for ongoing solicited AEs will remain missing and not be imputed.

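### An SAE or AESI that began after D29 but has an incomplete start date is counted in the within-28-days safety tables, even when its recorded month or visit rules that window out

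*SAP*

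**What the plan says.** SAP 4.2.2.2.4 gives the formula "Time of Onset = start date of the unsolicited AE - date of last vaccination before the unsolicited AE + 1" and says that the within-28-days analysis "corresponds to AEs with a time of onset between 1 and 29 days". A note at the end of that section takes a fully dated event with a later onset out of the analysis and into a separate listing.

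For incomplete dates the section says: "The time of onset is considered as missing only if one or both dates are missing or partially missing". An event with missing onset is then "considered to have occurred just after the last vaccination (computed according to the Section 4.2.2.2.4), so will be included in these tables".

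Under SAP 4.2.2.2.3, when the start date is incomplete, the visit number in the Appeared after Visit field "is used to determine the last vaccination before the unsolicited AE". No other use of that field is given. Protocol 7.1 confirms the single dose: "Not applicable as there is only one vaccination".

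SAP 5.3.2.5 adds: "Missing or partially missing start dates or end dates for unsolicited AEs (including SAEs) will remain missing and not be imputed". It then brings unsolicited AEs with missing onset into the analyses by last vaccination. SAP 4.2.2 defines an SAE as a kind of unsolicited AE. SAP 4.2.2.4 and 4.2.2.5 divide SAEs and AESIs into a within-28-days period and a later one, "During the period from 29 days after the injection until the last participant contact at M6". SAP 4.2.2.4 adds a whole-study period for related SAEs. Neither section has its own rule for incomplete dates. Table 7.8 reports SAEs, deaths, AESIs and medically attended AEs within 28 days, in the 6-month follow-up period, and during the study.

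**The concern.** The default suits events that are collected only for 28 days. It is also applied to events that are collected for much longer: AESIs and all SAEs to month 6, and related or fatal SAEs to 5 years (Protocol 8.3.1). For these, a date that lacks only the day usually still shows whether onset could have fallen on D01-D29. The rule sets that information aside.

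The 28-day window is the one that matters clinically. Protocol 2.3.1 names it as the observation period for viscerotropic and neurotropic disease, and Protocol 10.3.6 sets additional investigations for suspected cases within it. The protocol expects such disease to be very rare in a trial, so a single event placed in the window by convention could change how one arm is described.

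**Working it through.** **No figure to reproduce.** The plan states no number on this point. The check applies the stated rules to example dates and then sizes one misplaced event.

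**1. The window.** An event 28 days after vaccination has onset 28 + 1 = 29 and is inside. An event 29 days after has onset 30 and is outside. The within-28-days period and the later period therefore meet without a gap or an overlap. The window itself is sound.

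**2. The same event with and without the day.** Assume vaccination on 10 January 2022 (illustrative).

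| Recorded start | Possible onset days | With a full date | With the day missing |
|---|---|---|---|
| May 2022 (month 4) | 112 to 142 | outside 28 days | counted within 28 days |
| January 2025 (about year 3) | 1088 to 1118 | outside 28 days | counted within 28 days |

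For the first row, 1 May 2022 is 111 days after 10 January 2022, so the earliest onset is 111 + 1 = 112.

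**3. Does this depend on the vaccination date?** No. The first of a month is at most 30 days before any other day in it. A month-only date covering day +120 therefore has an earliest onset of 120 - 30 + 1 = 91. One covering day +1080 has 1080 - 30 + 1 = 1051. Running 365 consecutive vaccination dates gives the same minima. Both are far above 29, so month and year alone exclude the window.

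**4. Where the default is reasonable.** With the same vaccination date, a start recorded only as February 2022 allows onset from day 22 + 1 = 23 to day 49 + 1 = 50. The window cannot be excluded from the date, so the default is defensible unless the visit field settles it.

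**5. Why the visit field does not help as written.** Its only role is to identify the last vaccination. With one dose, every post-vaccination event points to D01, whether it appeared after Visit 1 or after Visit 8. An event that the field places before vaccination is the only exception.

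**6. Which events are reached.** Non-serious unsolicited AEs are collected from D01 to D29 (Protocol 8.3.1), so for them the window is the collection period. What remains is SAEs (including fatal and serious medically attended events) and AESIs with onset after D29. A month-4 case would be an SAE or an AESI. A year-3 case would be a related or fatal SAE.

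**7. Size of one misplaced event.** These use the planned group sizes (SAP 5.5) and Clopper-Pearson 95% intervals, the SAP's method for safety proportions.

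| Arm | True count | With one misplaced event |
|---|---|---|
| vYF | 0/460 = 0% (0 to 0.80%) | 1/460 = 0.22% (0.01 to 1.21%) |
| Stamaril | 0/230 = 0% (0 to 1.59%) | 1/230 = 0.43% (0.01 to 2.40%) |

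**The case against.** The best defence is that this is a deliberate conservative convention. No date is invented, onset is displayed as missing, both arms are treated alike, and safety is descriptive with no hypothesis tested, so the primary conclusion cannot be affected. The events concerned are also the best documented in the trial. SAEs are reported within 24 hours and updated (Protocol 8.3.1), reconciled with the pharmacovigilance database (SAP 4.2.2), and covered by data review before lock (SAP 5.6). An SAE that still lacks a start day after all that should be rare. This stands, and it limits the weight of the point. It does not justify the rule where recorded data exclude the window, because there the default overrides information instead of covering for its absence.

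A reader might also infer stronger things that the documents do not support:

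- *That the rule misplaces AEs generally.* It does not, because non-serious unsolicited AEs are collected only to D29.
- *That a late event vanishes from the period in which it occurred.* Related SAEs have their own whole-study period in SAP 4.2.2.4, and Table 7.8 has during-the-study rows for SAEs, deaths, AESIs and medically attended AEs. For the period from 29 days to M6, the SAP does not say whether such an event is also counted there.
- *That SAP 5.3.2.5 expressly sends SAEs to the 28-day tables.* Its mention of SAEs belongs to the sentence on non-imputation. SAEs come under the 28-day rule through the definition in SAP 4.2.2, which is a sound inference but not an express statement.
- *That most incompletely dated serious events would be misplaced.* Such a percentage would need an assumed spread of onset over time and a known frequency of incomplete dates. The documents give neither.
- *That a year-3 event would change the 28-day table in the first report.* The first interim analysis uses cleaned, locked data to M6, and later results go into addenda (SAP 5.4). Such an event could matter only if the 28-day table is produced again later.

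**Conclusion.** The point holds in a limited form and is minor. As written, the SAP counts an SAE or AESI with onset after D29 and an incomplete start date as a 28-day event, even when the month and year or the visit field show this to be impossible. A fully dated twin of that event would be left out. This is a stated rule that gives a wrong count in Table 7.8, not a missing detail.

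The overall effect cannot be estimated, because the number of incomplete dates is unknown and probably small. The 0.22 and 0.43 percentage-point shifts are for one hypothetical event at planned enrolment, with no true event in the window. The conclusion rests on reading SAP 4.2.2.2.4 literally and on SAEs and AESIs having no date rule of their own.

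**What to change.** Amend SAP 4.2.2.2.4 and 5.3.2.5 as follows:

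- Count an event with an incomplete start date within 28 days only if the known month and year and the Appeared after Visit field are both compatible with onset on D01-D29.
- Otherwise assign it to the existing period from 29 days to M6 or, if later, only to the existing during-the-study rows. No new period is needed.
- Keep the just-after-vaccination default where neither item excludes the window.
- Footnote the number of events placed by default, by arm.

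The visit check should use the actual visit date. If Visit 4 took place on D29, an event later that day still has onset 29.

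The same edit can correct the cross-references. SAP 4.2.2.2.4 cites itself for the last vaccination and the daily-intensity section (4.2.2.1.1) for its date, while SAP 5.3.2.5 points to 4.2.2.2.3.

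The cost is a few sentences and one extra derivation step on fields the SAP already uses.

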## 4.2.2.2.5 **Duration**

Duration is derived from the start and end dates of the unsolicited AE:

Duration = End date of unsolicited AE - start date of unsolicited AE + 1.

The duration is considered as missing only if one or both of the start and end dates of the unsolicited AE is missing or partially missing.

Duration will be displayed by categories as 1-3 days, 4-7 days, 8-14 days, 15 days or more, missing.

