To describe the safety profile of the vYF vaccine in comparison to the safety profile of the control Stamaril To describe the safety of vaccination in all participants up to 28 days after vaccination To describe all serious adverse events (SAEs) up to 6-month follow-up To describe related SAEs and all deaths from D01 to 5 years after vaccination To describe all AESIs up to 6-month after vaccination;	
 
Presence, nature (Medical Dictionary for Regulatory Activities [MedDRA] preferred term), duration, intensity and relationship to vaccination of any unsolicited systemic AEs reported in the 30 minutes after vaccination
 
Presence, time to onset, number of days of presence, and intensity of solicited (pre-listed in the participant's diary and electronic case report form [eCRF]) injection site reactions up to 7 days after vaccination solicited
 
Presence, time to onset, number of days of presence, and intensity of solicited systemic reactions up to 14 days after vaccination
 
Presence, nature (MedDRA preferred term), time to onset, duration, intensity, and relationship to vaccination (for systemic AEs only) of unsolicited (spontaneously reported) AEs up to 28 days after vaccination
 

Objectives	Endpoints		
	
 
Presence of any SAEs and AESIs, up to 6-month after vaccination
 
Presence of related SAEs and all deaths from D01 to 5 years after vaccination
 
		
Exploratory			
To describe the serological status of FV infection (dengue and Zika in all participants in EU and Asia; JE in Asia) in the study population at baseline	NAb levels against FV infection (dengue and Zika in all participants in EU and Asia; JE in Asia) on a blood sample taken at baseline		

AESI: adverse event of special interest; D: day; eCRF: electronic case report form; FV: flavivirus; GMT: geometric means of titers; GMTR: geometric means of titer ratios; M: month; MN; microneutralization; NAb: neutralizing antibody; Y: year

- \* YF-naïve participants (or negative) at baseline correspond to participants with no detectable YF antibody (Ab) titers before vaccination. YF seronegative at baseline is defined as a titer < LLOQ for the assay (any participant with a baseline titer  $\geq$  LLOQ will be eliminated from the primary analysis [Per-protocol analysis]).
- LLOQ determined as 10 (1/dil), also defined the threshold of protection.

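### An event without a complete end date is tabulated with missing duration even when the recorded data already prove that it reached the top duration category

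*SAP*

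**What the plan says.** Protocol section 3 (Table 3.1) makes the following part of the secondary safety endpoints: "duration, intensity, and relationship to vaccination (for systemic AEs only) of unsolicited (spontaneously reported) AEs up to 28 days after vaccination". For solicited reactions the corresponding component is the number of days of presence, up to 7 days (injection site) or 14 days (systemic).

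The SAP derives three quantities.

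- **Unsolicited AEs (4.2.2.2.5).** Duration is end date − start date + 1. The missing-data rule is "The duration is considered as missing only if one or both of the start and end dates of the unsolicited AE is missing", extended to partial dates. The display is: "Duration will be displayed by categories as 1-3 days, 4-7 days, 8-14 days, 15 days or more, missing".
- **Solicited reactions within the solicited period (4.2.2.1.5).** The count comes from daily grades: "It corresponds to the number of days with daily intensities of Grade 1, Grade 2, or Grade 3". No end date is needed. The top categories are 8 days (injection site) and 15 days (systemic).
- **Solicited reactions, overall days (4.2.2.1.6).** This applies to reactions ongoing when the solicited period ends. "If the end date is missing or incomplete (contains missing data), the overall number of days of presence will be considered as Missing". The categories are "Injection site reactions: 2-3 days, 4-7 days, 8 days or more, missing end date" and "Systemic reactions: 2-3 days, 4-7 days, 8-14 days, 15 days or more, missing end date".

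Section 5.3.2.5 rules out imputation of unsolicited AE dates and adds: "Missing or partially missing end dates for ongoing solicited AEs will remain missing and not be imputed". Section 4.2.2.1.7 derives an ongoing status for solicited reactions separately, from recorded intensities. No section assigns an event to a category by the minimum duration already established.

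**The concern.** An end date can be absent because the event had not resolved when the participant was last seen, or because the date was simply not recorded. The rule treats both alike. In the first case the duration is censored, not unknown: the record gives a lower bound, and that bound may already lie in the top category.

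The absence of an end date is plausibly related to duration. Protocol 8.3 and 8.3.3 require follow-up of AEs that are serious, related or led to discontinuation. No such requirement is stated for other AEs, and non-serious unsolicited AEs are collected only to D29 (8.3.1). Even a followed event may end as stable or chronic, and the SAP does not say whether a chronicity date counts as an end date.

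What is at stake is the row that a safety reader of a new live vaccine looks at for prolonged events. For unsolicited AEs the missing row pools proven long events with unknown start dates and clerical gaps, so the reader cannot tell how many events are known to have lasted 15 days or more. The outcome summary (SAP 4.2.2.10) carries no duration.

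**Working it through.** The documents give no figure for AE duration or for the frequency of missing end dates, so there is no planned number to reproduce. The check applies the SAP's own formulas.

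**1. Unsolicited AEs.** Minimum duration = day last documented as present − onset day + 1 (the 4.2.2.2.5 formula with the last documented day in place of the end date). For an event unresolved at a visit on D29:

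| Onset | Minimum duration | Proven 15 days or more? | SAP row |
|---|---|---|---|
| D1 | 29 − 1 + 1 = 29 | yes | missing |
| D10 | 29 − 10 + 1 = 20 | yes | missing |
| D15 | 29 − 15 + 1 = 15 | yes | missing |
| D16 | 29 − 16 + 1 = 14 | no | missing |
| D20 | 29 − 20 + 1 = 10 | no | missing |

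Onset by D15 is therefore the boundary for a visit held on D29.

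**2. Solicited reactions, checking the formula.** SAP 4.2.2.1.6: (end date − vaccination date) + days present in the period − period length + 1. The length is 8 for injection site (D1–D8) and 15 for systemic (D1–D15).

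- Injection site, D1 to D12: (12 − 1) + 8 − 8 + 1 = 12. Correct.
- Injection site, D8 to D10: (10 − 1) + 1 − 8 + 1 = 3. Correct.
- Systemic, D15 to D16: (16 − 1) + 1 − 15 + 1 = 2. Correct.

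**3. Solicited reactions, lower bound.** Status *Ongoing* under 4.2.2.1.7 needs at least Grade 1 on the last solicited day and at least Grade 1 as the maximum afterwards. The reaction then extends at least one day past the period. With length L and d days present, the earliest possible end day is L + 1, so the minimum is (L + 1 − 1) + d − L + 1 = d + 1. The lowest category in 4.2.2.1.6, which starts at 2 days, agrees with this for d = 1.

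- Injection site present on all 8 days: at least 8 + 1 = 9.
- Systemic present on all 15 days: at least 15 + 1 = 16.

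Without an end date, the first is shown as 8 days under 4.2.2.1.5 but not as 8 days or more under 4.2.2.1.6. The second is treated the same way at 15 days.

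**4. Illustration of size (assumed inputs only).** Suppose 100 unsolicited AEs, of which a true share q last 15 days or more. A fraction f of those long events lack an end date, and no other event does. The top row shows q(1 − f) of all AEs, or q(1 − f)/(1 − qf) of AEs with known duration. The missing row shows qf.

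| q | f | Top row, of all | Top row, of known | Missing row |
|---|---|---|---|---|
| 10% | 10% | 9.0% | 9.1% | 1.0% |
| 10% | 25% | 7.5% | 7.7% | 2.5% |
| 10% | 50% | 5.0% | 5.3% | 5.0% |
| 30% | 50% | 15.0% | 17.6% | 15.0% |

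Of all AEs, the top and missing rows together always return q. In general the missing row also holds short events, so the sum is a ceiling on the true share.

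**The case against.** A reader might infer that the longest events drop out of the tables and that the duration endpoints are biased short. The documents do not support this, for five reasons.

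- **Nothing is dropped.** Each affected table has its own missing row. SAP Table 5.1 specifies counts and percentages for safety, with no mean or median duration in which a shortfall could hide.
- **The protocol's solicited endpoint is intact.** Days of presence within 7 or 14 days come from daily grades. A reaction present on every solicited day reaches the top category of 4.2.2.1.5 whatever its end date. Only the supplementary overall count is touched.
- **A missing end date does not identify a long event.** The D15–D16 systemic reaction above lasts 2 days, and an AE starting on D20 and unresolved on D29 is known only to have lasted at least 10.
- **Follow-up is better than might be assumed.** Protocol 8.3.3 does not end follow-up at Visit 4. For related AEs and AEs leading to discontinuation it requires follow-up to resolution, stability or chronicity, with the date of disappearance or chronicity reported.
- **No arm difference follows from the rule.** It is the same in both groups, and the secondary analyses are descriptive.

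All five stand, and they limit the point to one of presentation. They do not answer the remainder: where continued presence is documented, the SAP reports as missing a category that its own data establish. That also sits oddly with its other conventions. A reaction too large to measure is Grade 3 (4.2.2.1.1), a missing relationship counts as related (5.3.2.2), and an AE with missing onset is kept in the tables (4.2.2.2.4).

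**Conclusion.** The point holds as a low-cost, minor improvement to a descriptive analysis. The rows for 15 days or more (unsolicited AEs) and for 8 or 15 days or more (overall days, solicited reactions) can be understated, because events with a proven minimum in that category are shown as missing. The understatement is at most the missing row. Its actual size depends on how many end dates are missing and for which events, which the documents do not say; the percentages in the illustration are assumptions. That missingness rises with duration is plausible from the follow-up rules but not established.

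The named endpoint concerned is unsolicited AE duration. The within-period solicited endpoint and the primary non-inferiority analysis do not change.

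**What to change.** Amend SAP 4.2.2.2.5, 4.2.2.1.6 and 5.3.2.5 as follows.

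1. **Unsolicited AEs with a complete start date, recorded as not resolved.** Compute minimum duration = last visit or contact date at which the event is documented as present − start date + 1. With a partial end date, use the earliest date compatible with it.
2. **Solicited reactions classed as *Ongoing* under 4.2.2.1.7 with a missing end date.** Use days of presence in the solicited period + 1. Do not add the day in any other case: 4.2.2.1.7 deliberately sets aside the investigator's ongoing flag, so the extra day would be unproven.
3. **Classification.** If the minimum reaches the top category (15 days for unsolicited AEs and systemic reactions, 8 for injection-site reactions), count the event there. Otherwise show it as ongoing for at least x days, in a row apart from unknown dates.
4. **All other missing dates** stay missing.

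The cost is a few lines of text and a little programming, and the duration figures may look slightly less favourable. For rule 1 the sponsor should confirm that the case report form links an unresolved event to a visit or contact date. The documents show that outcome and visit dates are available, but not that a per-event date of last presence is collected. Where that link is absent, the event stays in the missing row.
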